Protocol	Date	Description of	Brief rationale
Version		changes	
Version 1.0	2022-07-25	NA	NA
(Original			
Protocol)			
,			

Protocol History/Amendment Summary

Abbreviations and Acronyms

- AE Adverse event
- API Application programming interface
- CAD Computer-assisted detection
- CRF Case report form
- CXR Chest X-Ray
- DFAT Department of Foreign Affairs and Trade, Government of Australia
- DNA Deoxyribonucleic acid
- DR-TB Drug resistant TB
 - DST Drug susceptibility testing / Drug sensitivity testing
- GCLP Good clinical laboratory practice
- GCP Good clinical practice
- HCW Healthcare worker
- HIV Human Immunodeficiency Virus
- ICH International Council for Harmonisation of Technical Requirements for Pharmaceuticals for Human Use
 - ID Identifier
- IEC Independent ethics committee
- IRB Institutional review board
- IT Information technology
- MDR-TB Multidrug-resistant tuberculosis
 - MTB Mycobacterium tuberculosis
 - MTBC Mycobacterium tuberculosis complex
 - PCR Polymerase chain reaction
 - PI Principal investigator
 - PICF Participant information and consent form
 - POC Point of care
- PRIME-TB Papua New Guinea and Republic of Indonesia for Micro-elimination of TB, an Australian department of foreign affairs and trade (DFAT) Centre for Health Security funded project
 - RIF Rifampicin
 - SAE Serious adverse event
 - SAP Statistical analysis plan
 - SIM Subscriber identity module
 - SMS Short message service
 - SOC Standard of care
 - SOP Standard operating procedure
 - TB Tuberculosis
 - UGM Universitas Gadjah Mada
 - USD United States dollar
 - WHO World Health Organization
 - WIFI Wireless technology
 - ZTBI YY Zero TB Initiative Yogyakarta

1 Research Outline

Title	Localised mobile a ctive case finding with T ruenat molecular testing for the e ffective diagnosis of tuberculosis (LOCATE-TB)		
Protocol version and date	Protocol version 1 (2022-06-28)		
Primary objective(s)	Assess the operational feasibility and acceptability of use of Truenat MTB Plus and MTB-RIF Dx testing on the Molbio Truenat platform within a mobile TB active case finding service in Yogyakarta, Indonesia		
Secondary objective(s)	 Within a community mobile active TB case finding service: 1. For bacteriologically confirmed tuberculosis cases, compare time to result for individuals diagnosed using decentralised Truenat MTB plus and MTB-RIF Dx against time to result for individuals diagnosed using centralised geneXpert testing 2. Compare the time to treatment commencement for decentralised Truenat MTB Plus and MTB-RIF Dx to centralised Xpert testing 		
Primary endpoints (outcomes)	 The operational feasibility of point-of-care Truenat MTB Plus and MTB-RIF Dx will be assessed by: Adequacy of Truenat MTB Plus and MTB-RIF Dx training as measured by post-training assessment Operational performance of Truenat MTB Plus and MTB-RIF Dx as measured by platform failure rates and error rates Instrument user and health service provider views regarding feasibility and acceptability of Truenat MTB Plus and MTB-RIF Dx performed within a mobile active TB case finding service Screening participant views regarding acceptability of point-of-care Truenat MTB Plus performed within mobile active TB case finding service 		
Secondary endpoints (outcomes)	 Reduction in time to result for those tested with Truenat MTB Plus and MTB-RIF Dx For those with positive result on Truenat MTB Plus or GeneXpert (standard of care) the median time from initial assessment to TB treatment initiation 		

Trial design	This is a prospective mixed methods implementation science study to evaluate the use of decentralised Truenat MTB Plus and MTB-RIF Dx within a mobile active TB case finding service.
	For the primary endpoints the design for each component will be:
	1a – application of a performance test to assess laboratory staff performance of trainees immediately after initial training
	1b – Platform failure and error rates calculated from platform logs
	1c – Survey of laboratory staff and health care workers on acceptability and operational challenges of decentralised Truenat MTB Plus and MTB-RIF Dx testing
	1d – In-depth qualitative interviews of screening participants using purposive sampling to include a diversity of sex, age, whether tested microbiological positive or negative; and among contacts of known TB cases and community participants.
	For the secondary endpoints a randomised of decentralised microbiological testing using Truenat MTB Plus and MTB-RIF Dx (Truenat arm) compared with centralised GeneXpert testing (standard of care arm) will be conducted. Screening days will be randomised 1:1 to Truenat or standard of care.
Trial sites / setting	Indonesia has an estimated TB incidence of 301 per 100,000 population. The TB treatment coverage (notified/estimated incidence) in 2020 was 47%, with 52% of diagnosed cases bacteriologically confirmed.
	The Zero TB Initiative, Yogyakarta (ZTBI YY), is a partnership between Universitas Gadjah Mada, the TB program Yogyakarta, TB stakeholders in Yogyakarta and the Burnet Institute Melbourne. ZTBI YY includes a mobile community based active TB case finding service within Kulon Progo Regency (estimated 2021 population of 442 382), Yogyakarta City (estimated 2021 population of 415 382) in Yogyakarta, Indonesia, and Sleman Regency (estimated 2021 population of 1 087 339). The service which commenced in 2020, consists of a mobile van chest X-ray (CXR) based TB screening program covering all districts in these 2 sites. Potential 'hotspot' sites for screening are identified based on TB program records of previously reported TB cases within the preceding 3 years. Designated sites for screening are identified more than 2 weeks in advance to allow time to notify relevant authorities and the community near the intended screening site of the service and the free access to screening for TB. Community mobilisation is conducted by trained community cadres in collaboration with local community leaders and in consultation with the Dinas Keschatan. Screening consists of symptom screening and CXR with computer aided diagnosis (CAD) software reading of CXR using the qXR (QURE.ai, Mumbai, India). Those identified as a screen positive, either with reported symptoms on symptom screen or positive CXR on qXR, have 1 spot

	sputum collected for molecular testing (currently at centralised laboratories on the
	GeneXpert platform with Xpert MTB/RIF cartridges).
	Household contacts of notified TB cases are screened for symptoms, undergo tuberculin
	skin testing and are referred for CXR at mobile screening or at the nearest CXR facility.
	Those screening positive on symptoms or CXR are asked to provide a spot sputum
	sample for molecular testing.
Trial population	The trial population includes different groups for different objectives and endpoints:
	• Laboratory staff and heath care workers trained to perform Truenat Mtb Plus
	and MTB-RIF Dx (1a)
	• Healthcare workers and laboratory staff involved in the use of Truenat Mtb Plus
	and MTB-RIF Dx (1c)
	• Screening participants (1d, 2, 3)
	The trial population for objectives 2 and 3 consists of participants attending case finding
	services in Sleman District and Yogyakarta City in Yogyakarta Province who screen
	positive for TB. These participants will consist of residents of identified hotspot screening
	areas, and household contacts of microbiologically confirmed index ${\rm TB}$ cases.
Sample Size	Operational Feasibility and Acceptability
Sample Size	Operational Feasibility and Acceptability 1. Post-Training Assessment: All laboratory staff and health care workers trained in performance of Truenat MTB Plus (2 laboratory staff and 8–10 non laboratory staff)
Sample Size	 Operational Feasibility and Acceptability 1. Post-Training Assessment: All laboratory staff and health care workers trained in performance of Truenat MTB Plus (2 laboratory staff and 8–10 non laboratory staff) 2. Feasibility and HCW acceptability: Survey of all health care workers involved in the mobile screening service (10-15 HCWs including nurses, doctors and program staff)
Sample Size	 Operational Feasibility and Acceptability 1. Post-Training Assessment: All laboratory staff and health care workers trained in performance of Truenat MTB Plus (2 laboratory staff and 8–10 non laboratory staff) 2. Feasibility and HCW acceptability: Survey of all health care workers involved in the mobile screening service (10-15 HCWs including nurses, doctors and program staff) 3. Screening participant acceptability: purposive sampling representative of age groups, sex, bacteriological positivity and indication for screening (community screening or contact investigation) with 18-24 participants
Sample Size	 Operational Feasibility and Acceptability 1. Post-Training Assessment: All laboratory staff and health care workers trained in performance of Truenat MTB Plus (2 laboratory staff and 8–10 non laboratory staff) 2. Feasibility and HCW acceptability: Survey of all health care workers involved in the mobile screening service (10-15 HCWs including nurses, doctors and program staff) 3. Screening participant acceptability: purposive sampling representative of age groups, sex, bacteriological positivity and indication for screening (community screening or contact investigation) with 18-24 participants Randomised Comparison (secondary endpoint 2)
Sample Size	 Operational Feasibility and Acceptability 1. Post-Training Assessment: All laboratory staff and health care workers trained in performance of Truenat MTB Plus (2 laboratory staff and 8–10 non laboratory staff) 2. Feasibility and HCW acceptability: Survey of all health care workers involved in the mobile screening service (10-15 HCWs including nurses, doctors and program staff) 3. Screening participant acceptability: purposive sampling representative of age groups, sex, bacteriological positivity and indication for screening (community screening or contact investigation) with 18-24 participants Randomised Comparison (secondary endpoint 2) The mobile service screens 1000 people per month with 12.1% of participants in rural
Sample Size	 Operational Feasibility and Acceptability Post-Training Assessment: All laboratory staff and health care workers trained in performance of Truenat MTB Plus (2 laboratory staff and 8–10 non laboratory staff) Feasibility and HCW acceptability: Survey of all health care workers involved in the mobile screening service (10-15 HCWs including nurses, doctors and program staff) Screening participant acceptability: purposive sampling representative of age groups, sex, bacteriological positivity and indication for screening (community screening or contact investigation) with 18-24 participants Randomised Comparison (secondary endpoint 2) The mobile service screens 1000 people per month with 12.1% of participants in rural areas screening positive and requiring microbiological examination of sputum samples.
Sample Size	 Operational Feasibility and Acceptability 1. Post-Training Assessment: All laboratory staff and health care workers trained in performance of Truenat MTB Plus (2 laboratory staff and 8–10 non laboratory staff) 2. Feasibility and HCW acceptability: Survey of all health care workers involved in the mobile screening service (10-15 HCWs including nurses, doctors and program staff) 3. Screening participant acceptability: purposive sampling representative of age groups, sex, bacteriological positivity and indication for screening (community screening or contact investigation) with 18-24 participants Randomised Comparison (secondary endpoint 2) The mobile service screens 1000 people per month with 12.1% of participants in rural areas screening positive and requiring microbiological examination of sputum samples. We will enrol participants for a minimum of 6 months and a maximum of 9. Which
Sample Size	 Operational Feasibility and Acceptability Post-Training Assessment: All laboratory staff and health care workers trained in performance of Truenat MTB Plus (2 laboratory staff and 8–10 non laboratory staff) Feasibility and HCW acceptability: Survey of all health care workers involved in the mobile screening service (10-15 HCWs including nurses, doctors and program staff) Screening participant acceptability: purposive sampling representative of age groups, sex, bacteriological positivity and indication for screening (community screening or contact investigation) with 18-24 participants Randomised Comparison (secondary endpoint 2) The mobile service screens 1000 people per month with 12.1% of participants in rural areas screening positive and requiring microbiological examination of sputum samples. We will enrol participants for a minimum of 6 months and a maximum of 9. Which would result in between 3000–4500 persons screened in each arm (Truenat arm or
Sample Size	 Operational Feasibility and Acceptability 1. Post-Training Assessment: All laboratory staff and health care workers trained in performance of Truenat MTB Plus (2 laboratory staff and 8–10 non laboratory staff) 2. Feasibility and HCW acceptability: Survey of all health care workers involved in the mobile screening service (10-15 HCWs including nurses, doctors and program staff) 3. Screening participant acceptability: purposive sampling representative of age groups, sex, bacteriological positivity and indication for screening (community screening or contact investigation) with 18-24 participants Randomised Comparison (secondary endpoint 2) The mobile service screens 1000 people per month with 12.1% of participants in rural areas screening positive and requiring microbiological examination of sputum samples. We will enrol participants for a minimum of 6 months and a maximum of 9. Which would result in between 3000–4500 persons screened in each arm (Truenat arm or standard of care centralised GeneXpert arm). Consequently, per the calculations below,
Sample Size	 Operational Feasibility and Acceptability Post-Training Assessment: All laboratory staff and health care workers trained in performance of Truenat MTB Plus (2 laboratory staff and 8–10 non laboratory staff) Feasibility and HCW acceptability: Survey of all health care workers involved in the mobile screening service (10-15 HCWs including nurses, doctors and program staff) Screening participant acceptability: purposive sampling representative of age groups, sex, bacteriological positivity and indication for screening (community screening or contact investigation) with 18-24 participants Randomised Comparison (secondary endpoint 2) The mobile service screens 1000 people per month with 12.1% of participants in rural areas screening positive and requiring microbiological examination of sputum samples. We will enrol participants for a minimum of 6 months and a maximum of 9. Which would result in between 3000–4500 persons screened in each arm (Truenat arm or standard of care centralised GeneXpert arm). Consequently, per the calculations below, the sample will be sufficiently powered to detect a difference in median time to result of

of 211 microbiological examinations in each arm. Throughput in of 3000–4500 persons would be expected to result in 363–544 microbiological examinations in each arm.

	Median time to result standard of care	Median time to result Truenat	Alpha	Power	Sample size per arm	
	3 (sd = 14)	1 (sd = 14)	0.05	0.8	29	
	3 (sd = 21)	1 (sd = 21)	0.05	0.8	34	
	3 (sd = 14)	2 (sd = 14)	0.05	0.8	175	
	3 (sd = 21)	2 (sd = 21)	0.05	0.8	211	
Eligibility criteria for	Inclusion Crite	eria:				
randomised comparison	 Peop Slema Able as par Exclusion cri Cann Curre Patier Patier 	 clusion Criteria: People aged 12 years old or above presenting to mobile CXR based screening in Sleman district and Yogyakarta City Able and willing to consent. For adolescents aged 12-17, verbal consent as well as parental/guardian informed consent will be required Exclusion criteria: Cannot provide sputum Currently receiving anti-TB therapy Patients who are seriously ill and need to be admitted to hospital Patients with potential COVID-19 referred for further assessment 				
Eligibility Criteria	1. Post-	Training Assess	sment (Object	tive 1a): All lab	ooratory staff and h	ealth care
operational feasibility and	work	ers trained in po	errormance of	ruenat assay	s who consent to p	barticipate
acceptability assessments	2. Feasi mobi	bility and HCW le screening ser	acceptability	(Objective 1c) sent to particir	: All HCW involve pate.	d in the
	3 Scree	ning particinan	t accentability	(Objective 1d). Adults 18 years of	of age or older
	who	screened positiv	ve for presum	ptive TB in the	e active case finding	g program
	within	n the preceding	1 week and p	provide inform	ed consent; and pa	rents and

	legal guardians who have a child aged 12 to 17 years that screened positive for presumptive TB in the active case finding program within the preceding 1 week and provide informed consent.		
Study Timeline	Ethics Clearance	Q3 2022	
	Importation	Q3 2022	
	Training + post training Assessment	Q4 2022	
	Participant enrolment	Q4 2022–Q2 2023	
	Data Cleaning + analysis	Q3 2023	
	Total duration 12 months		

2 Study Schedule of Events

Procedure	Day 1	Day 1-3	Day 7-21
Informed consent	×		
Eligibility assessment	x		
Enrolment	x		
Contact information	x		
Medical history + screening assessment	x		
TB diagnosis assessment	x		x
Referral to health facility for treatment based on Truenat MTB		x	
Plus and MTB-RIF Dx result			
Collection of data from health facilities and laboratory			x
Interview with selected participants for user acceptability			x

3 Introduction

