3.3 Molbio Truenat Mtb Plus and MTB-RIF Dx

Molbio Truenat MTB Plus and MTB-RIF Dx (Truenat) are chip-based point-of-care rapid molecular assays for the detection of tuberculosis. The Truenat MTB Plus assay uses two devices — the first to extract and purify DNA (Trueprep Auto v2 Universal Cartridge-based Sample Prep Device) and the second (Truelab Real Time micro PCR Analyzer) to conduct PCR analysis to report a semi-quantitative result for MTBC. A positive sample can be loaded onto an additional chip (MTB-RIF Dx) for detection of rifampicin resistance. The Truelab Micro PCR Analyzer is portable, battery-powered and can provide a result in an hour. FIND's "real-world" multicentre diagnostic accuracy study has reported that "Truenat MTB, MTB Plus and MTB-RIF Dx assays have similar accuracy to Xpert MTB/RIF and can be performed at the primary healthcare centre level". (Penn-Nicholson, et al., 2021)

The Truenat MTB Plus and MTB-RIF Dx assays are WHO-endorsed with recommendations for use in adults and children with signs and symptoms of pulmonary TB. In the real-world multicentre study Truenat was reported as having a pooled sensitivity of 80% (75–84) and 96% (95–97) specificity when performed at primary health centres. (Penn-Nicholson, et al., 2021) In a comparison from sites where Truenat assays were conducted in parallel with GeneXpert MTB/RIF on the same specimens the authors reported no significant difference irrespective of smear status. (Penn-Nicholson, et al., 2021)

Devices	Throughput per 8-hour shift with optimized work flow ³	Estimated throughput with "real-world" conditions
1 Trueprep Device + 1 Truelab Analyzer Uno	10-12 specimens	7-9 specimens
1 Trueprep Device + 1 Truelab Analyzer Duo	20-24 specimens	15-18 specimens
2 Trueprep Devices + 1 Truelab Analyzer Quattro	40-48 specimens	30-36 specimens

TRUENAT DEVICE COMBINATIONS AND SAMPLE THROUGHPUT

The Truenat PCR Analyzer is able to transfer data wirelessly in real time using a SIM card, WIFI or Bluetooth. Results can be sent by SMS or email to clinicians as well as to electronic patient and lab information systems (via a customised API), or through extraction of the data in text delimited format. The analyser can store up to 20 000 results in internal memory

Chips (at temperatures between 2°C and 30°C) and the sample preparation reagents (at temperatures between 2°C and 40°C) have a shelf-life of 2 years. The chips can be stored for up to 6 months at temperatures between 30°C and 40°C.

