- For decentralised **Truenat**, two spot sputum samples will be collected and the participant will be informed that their sample will be tested on the day, and will be asked if they prefer to wait for the result or be contacted when the result is available.
 - Where a patient has a positive result on Truenat MTB Plus, the Truenat MTB-RIF Dx assay will be performed to test for rifampicin resistance. Patients with a positive result on Truenat MTB Plus will be informed of the result and advised to attend the nearest puskesmas or hospital for counselling and commencement of TB treatment, or referral to another facility of their choice for treatment.
 - Those testing negative for MTB will have their case reviewed by a doctor at the catchment health facility to determine if they need further follow up in accordance with the standard ACF protocols; and taking into consideration the result of the GeneXpert MTB/RIF assay
 - Due to National Tuberculosis Program requirements all patients tested with Truenat will also be tested with GeneXpert MTB/RIF using the second spot sputum sample. Treatment will be initiated based on positive Truenat or GeneXpert Mtb/RIF result, with review by the TB active case finding service doctor of cases where the result is discordant.
 - Commencement of TB treatment will be according to standard national TB protocols. Further clinical care and diagnostic investigations will be provided within governmental health care services. If a patient wishes to seek further care at a specific health facility or service of their choosing they will be provided with a referral.

The testing and treatment algorithm for patients in the Truenat Arm

Follow-Up Interview

Participants will be called at a 14-day phone visit (+/- 7 days). Three attempts will be made to contact a participant by phone. In the event that the participant is still not contacted, a phone call to the agreed trusted contact will be made to find out about the participant's whereabouts and to ask if they can arrange for the participant to return a call or to be visited at an acceptable time. A home visit will be conducted for those participants who cannot be reached by phone or who identify that they prefer a home visit or do not have access to a phone.

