5.9 Sample Size

5.9.1 Objective 1: Operational Feasibility and Acceptability

1a Post-Training Assessment

All laboratory staff trained in performance of Truenat who consent to participate in the study: 2 laboratory staff and 8 non-laboratory staff will be subject to analysis using post-training proficiency assessment, and questionnaire response.

1b Operational performance

The sample size for failure and unavailability will be the total number of hours that the platform is planned to be used and available (i.e., the total hours across all screening days when decentralised Truenat is assigned); and the total number of tests allocated to the Truenat arm irrespective of whether or not the test could be performed. The sample size for test errors is the total number of assays performed using decentralised Truenat.

1c Feasibility and HCW acceptability

The survey of all HCW involved in the mobile screening service is expected to yield a sample size of (10-15 HCW staff including nurses, doctors, and program implementers).

1d Screening participant acceptability

Purposive sampling will be used to target the selection of 30 participants for in-depth interviews on test feasibility and acceptability. Critical cases will be selected to represent both those given a positive TB result by Truenat and a negative TB result, those who waited for their results and those who did not wait. Quotas will be used to include males and females, a range of ages, and a range of different screening population characteristics (urban vs rural, risk population).

The above sample size estimations for in-depth interviews are approximations only and provide a guide. The approach for this qualitative analysis is exploratory –therefore, should information be revealed that requires exploration with other groups (e.g. community leaders), then additional in-depth interviews may be undertaken.

5.9.2 Objectives 2 and 3: Randomised comparison of decentralised Truenat MTB Plus and MTB-RIF Dx to standard of care

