The mobile service screens 1000 people per month with 12.1% of participants in rural areas screening positive and requiring microbiological examination of sputum samples. We will enrol participants for a minimum of 6 months and a maximum of 9. Which would result in between 3000–4500 persons screened in each arm. Consequently, per the calculations below, the sample will be sufficiently powered to detect a difference in median time to result of one or more days with an alpha of 0.05 and power of 0.8. This would require a minimum of 211 microbiological examinations in each arm. Throughput in of 3000–4500 persons would be expected to result in 363–544 microbiological examinations in each arm.

Median time to result standard of care	Median time to result Truenat	Alpha	Power	Sample size per arm
3 (sd = 14)	1 (sd = 14)	0.05	0.8	29
3 (sd = 21)	1 (sd = 21)	0.05	0.8	34
3 (sd = 14)	2 (sd = 14)	0.05	0.8	175
3 (sd = 21)	2 (sd = 21)	0.05	0.8	211

These assumptions are based on the current active case finding TB diagnostic cascade from the PRIME-TB/TB REACH project in Yogyakarta in 2020 and 2021, which includes the impact of COVID-19 on activities.

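### Time to treatment is compared only among test-positives, a group that forms after the screening day is allocated and differently in each arm, and the protocol's populations for both randomised endpoints conflict

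*Protocol*

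**What the plan says.** **Time to treatment (objective 3).** The synopsis endpoint is "For those with positive result on Truenat MTB Plus or GeneXpert (standard of care) the median time from initial assessment to TB treatment initiation". Section 4.2 restricts the comparison to bacteriologically confirmed cases. Table 1 in section 5.10 restricts it to participants whose initial molecular result was positive. Section 5.10.2 concedes that confirmed cases will be too few for adequate power, but still plans medians for the two groups and Kaplan-Meier curves by arm.

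**How each arm is tested.** Section 5.4.2 has two spot samples taken on Truenat days and states that "all patients tested with Truenat will also be tested with GeneXpert MTB/RIF using the second spot sputum sample". Treatment can follow a positive on either assay, and discordant results go to a doctor for review. Under standard of care, one spot sample goes to one central GeneXpert test (synopsis, trial setting; section 5.4.2).

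**Time to result (objective 2).** The synopsis objective limits it to bacteriologically confirmed cases. The synopsis endpoint is "Reduction in time to result for those tested with Truenat MTB Plus and MTB-RIF Dx", and section 5.7 also compares Truenat with centralised GeneXpert by assay. Sections 4.2 and 5.10.2 and Table 1 take all who were tested. Section 5.9.2 counts its sample size the same way: "This would require a minimum of 211 microbiological examinations in each arm", against throughput that "would be expected to result in 363–544 microbiological examinations in each arm".

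**The concern.** Randomisation by screening day makes the people who attend on the two kinds of day comparable. It does not make the people who later test positive comparable when the arms find positives by different means. A positive on a Truenat day may be someone whom a single test would have missed, or an extra false positive from the second test. Neither has a counterpart under standard of care. A difference in median time to treatment then mixes faster testing with a different group of patients.

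The unsettled membership of GeneXpert-only positives on Truenat days adds a bias whose direction can be guessed. They wait for the central result, which section 5.4.2 puts at 1–3 days for standard of care, and they then have a discordance review. They are probably the slower starters, so omitting them shortens the Truenat median.

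These are the only randomised comparisons in the study, and section 6.4 says that the results will inform government decisions on scale-up.

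**Working it through.** **1. The plan's own sample size, to establish its population.** Section 5.9.2 sets a target of "one or more days with an alpha of 0.05 and power of 0.8". A normal calculation on the day scale does not fit (6,923 per arm for 3 vs 2 days, SD 21). A two-sided log-normal calculation does:

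- Log-variance s² for a given median and SD: s² = ln[(1 + √(1 + 4(SD/median)²))/2].
- Median 3, SD 21: s² = 2.017. Median 2, SD 21: s² = 2.399.
- n = (1.960 + 0.842)² × (2.017 + 2.399) / (ln 1.5)² = 210.8, so 211 per arm.

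The other rows (29, 34, 175) reproduce in the same way. The expected numbers are 0.121 × 3,000 = 363 and 0.121 × 4,500 = 544.5. The 211 is therefore a count of people tested. Were objective 2 run in confirmed cases, as the synopsis objective says, 211 per arm would need 211/544 = 39% to 211/363 = 58% of those tested to be confirmed. At an assumed 2–15% confirmed, power for 3 vs 2 days with SD 21 would be 0.08–0.41. In all tested it is 0.957–0.994, ignoring clustering by day.

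**2. Size of the positive group by arm.** Section 3.3 has Truenat "reported as having a pooled sensitivity of 80"%, with 96% specificity, and cites accuracy similar to Xpert. I assume the same values for GeneXpert and a prevalence p of 2–15%, which the protocol does not give.

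- One test: 0.80p + 0.04(1 − p).
- Either of two, independent errors: (1 − 0.2²)p + (1 − 0.96²)(1 − p) = 0.96p + 0.0784(1 − p).
- Example, n = 363 and p = 5%: one test 14.5 + 13.8 = 28.3 positives; either test 17.4 + 27.0 = 44.5; ratio 1.57.

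| Dependence between the tests | Ratio, either-positive to one-test, p = 15% to 2% |
|---|---|
| Full concordance | 1.0 |
| Halfway | 1.18–1.37 |
| Independent errors | 1.37–1.74 |

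With specificity 99% for both tests and independent errors, the ratio is 1.25–1.50.

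**3. Does a GeneXpert-only positive on a Truenat day count?**

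| Place | Reading |
|---|---|
| Synopsis endpoint | Ties GeneXpert to standard of care, so tends to leave them out |
| Table 1 | Requires an initial positive, so tends to leave them out |
| Section 4.2 | Bacteriologically confirmed, so in |
| Section 5.4.2 | Either positive can start treatment, so they are treated |

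Their share of the true cases detected on Truenat days, with 80% sensitivity for both tests:

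- Independent errors: (0.20 × 0.80)/0.96 = 0.16/0.96 = 16.7%. In the example above, 18.15 × 0.16 = 2.9 of 17.4 cases.
- Halfway: 0.08/0.88 = 9.1%.
- Full concordance: 0%.

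**4. If the by-assay wording were followed for time to result.** Suppose a share f of Truenat runs fails, those participants get standard-of-care timing, and they are left out. The arm's mean is then understated by f × (standard-of-care mean − Truenat mean). With mean = median × exp(s²/2) and SD 14, the means are 6.84 days (median 3), 3.81 (median 1) and 5.48 (median 2). For an assumed f of 5–20%:

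- Truenat median 1: 0.15–0.61 days in the mean, 0.06–0.29 in the median.
- Truenat median 2: 0.07–0.27 days in the mean, 0.04–0.18 in the median.

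The median shifts come from solving for the median of the two-part mixture.

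**The case against.** **Time to result is mostly defined on everyone tested.** This stands. A reader might infer that both randomised endpoints are restricted by test outcome and that the whole comparison loses the protection of randomisation. The documents do not support that. Sections 4.2 and 5.10.2, Table 1 and the sample size all use everyone tested, by group; only the synopsis objective restricts to confirmed cases. For objective 2 the finding is a conflict to reconcile.

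**Failed Truenat runs are not stated to be excluded.** This also stands. A reader might infer it from the by-assay wording, but section 5.1 assigns participants by screening day, section 5.10.2 accepts any molecular test, and the second sample gives a GeneXpert result. The phrase "irrespective of whether or not the test could be performed" in section 5.9.1 is a denominator for objective 1b and excludes nobody from objective 2. The shifts in step 4 are conditional on that reading.

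**Truenat-day positives need not contain a larger share of false positives because of the assay itself.** Such a contrast needs a GeneXpert specificity that the protocol does not give, and section 3.3 reports similar accuracy. The asymmetry that is documented is two tests against one.

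**Objective 3 is admitted to be underpowered, and the second test is a National Tuberculosis Program requirement.** Both are true. Low power does not remove selection, and the medians and curves will still be reported by arm. The double testing does limit any remedy: analysing all enrolled still compares two tests with one.

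**An SAP may add a by-arm analysis.** It may, but the conflicting populations are fixed in the protocol.

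**Conclusion.** The concern holds for time to treatment. The compared group depends on results obtained after allocation and is assembled differently by arm. Under the stated assumptions it could be 1.0 to about 1.7 times as large on Truenat days. Omitting GeneXpert-only positives would remove 0% to about 17% of detected true cases, probably in Truenat's favour. These ranges rest on assumed prevalence, equal accuracy of the two tests and unknown dependence between them. The documents give no basis for converting them into days of bias.

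For time to result, the protocol contradicts itself on population and on assay versus arm. The powered analysis is evidently meant for all tested. Some selection remains possible there too, since consent and sputum production follow allocation and Truenat days need two samples, but that is not selection on a test result.

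**What to change.** 1. State that both endpoints are analysed by the arm of the screening day.
2. **Objective 2:** all enrolled participants with a sample collected; time from collection to the first valid MTB result from any assay; failed Truenat runs stay in the Truenat arm. Align the synopsis objective, the synopsis endpoint and section 5.7 with section 5.10.2.
3. **Objective 3:** report by arm the proportion of all enrolled who started TB treatment by a fixed day, and the cumulative incidence of treatment start. Keep the median among positives as a description, including GeneXpert-only positives on Truenat days and showing them separately. Use one time origin: the synopsis counts from initial assessment, sections 5.7 and 5.10.2 from sample collection.
4. State that the comparison is of the strategies as delivered, Truenat plus GeneXpert on a second sample against one GeneXpert, and cannot separate test location from the second test.

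Cost: protocol wording only. Results and treatment data are already planned (sections 5.4.2 and 5.8.3, Table 1). The fixed day should be one that follow-up covers, given the call at day 14 ± 7 and the puskesmas records. The all-enrolled treatment endpoint will have few events and be imprecise, as section 5.10.2 already concedes for this objective.
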